3.2.2.3 Time from enrollment to electrical dysfunction, by lead subgroups**Lead Population**

All the leads without electrical dysfunction at enrollment within the Riata, Riata ST silicone, QuickSite/QuickFlex (1056T, 1058T, 1156T, 1158) and Durata lead groups

Analysis:

Time to electrical dysfunction will be analyzed using the Kaplan-Meier method. Those patients who do not experience an electrical dysfunction will be censored 3 years after enrollment in this trial. A separate Kaplan-Meier curve will be calculated for each of the lead subgroups outlined in Table 2.

For QuickSite/QuickFlex leads only, data from patients with an additional 1 year of follow-up will contribute to 2 separate lead subgroups (See Section 3.4.5).

3.2.2.4 Time from externalized conductors to electrical dysfunction, by lead subgroups**Lead Population**

All the leads with externalized conductors but without electrical dysfunction within the Riata, Riata ST silicone, QuickSite/QuickFlex (1056T, 1058T, 1156T, 1158) and Durata lead groups

Analysis:

Time to electrical dysfunction will be analyzed using the Kaplan-Meier method. The zero time will be the date at which externalized conductor was detected. Those patients who experience an externalized conductor after enrollment, but do not experience an electrical dysfunction will be censored 3 years after enrollment in this trial. A separate Kaplan-Meier curve will be calculated for each of the lead subgroups outlined in Table 2.

For QuickSite/QuickFlex leads only, data from patients with an additional 1 year of follow-up will contribute to 2 separate lead subgroups (See Section 3.4.5).

3.2.2.5 Time from other visual lead anomalies by each lead subcategory to electrical dysfunction, by lead subgroups**Lead Population**

All the leads with other visual lead anomalies (by each subcategory) but without electrical dysfunction within the Riata, Riata ST silicone, QuickSite/QuickFlex (1056T, 1058T, 1156T, 1158) and Durata lead groups

Analysis:

Time to electrical dysfunction will be analyzed using the Kaplan-Meier method. The zero time will be the date at which other visual lead anomaly (by each subcategory) was detected. Those patients who experience other visual lead anomaly (by each subcategory) after enrollment, but do not experience an electrical dysfunction will be censored 3 years after enrollment in this trial. A separate Kaplan-Meier curve will be calculated for each of the lead subgroups outlined in Table 2.

For QuickSite/QuickFlex leads only, data from patients with an additional 1 year of follow-up will contribute to 2 separate lead subgroups (See Section 3.4.5).

3.2.2.6 Adverse Event rate through 30 days post-intervention for lead (e.g. extraction, abandonment, revision, other)**Lead Population**

All the leads within the Riata, Riata ST silicone, QuickSite/QuickFlex (1056T, 1058T, 1156T, 1158) and

Durata lead subgroups that require an intervention/revision (e.g. extraction, abandonment, other)

Analysis

The 30-day adverse event rate will be calculated as the number of adverse events within 30 days associated with study lead related interventions in each of the 4 lead groups divided by total study lead related interventions in each of the 4 lead groups.

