*Expected attrition in each of the lead groups is based on the rationale provided above the table as well as larger attrition expected in older leads.

[figure not shown]
At enrollment, medical history, demographic data and lead measurement data will be collected. Additionally, cinefluoroscopy (AP, LAO 45° or the best possible LAO view, RAO 45° or the best possible RAO view) will be performed to determine the prevalence of lead compromise. A copy of

cinefluoroscopy performed as part of separate screening can be used to determine the prevalence of lead compromise as long as all three views (AP, LAO 45° or the best possible LAO view, RAO 45° or the best possible RAO view) are available. In patients with evidence of externalized conductors or other visual lead anomalies (fracture, subclavian crush, kink, broken filars on a shocking coil and other irregularities) the following chest x-rays or other available imaging studies will be collected (if available): a) earliest imaging study showing evidence of externalized conductors or other visual lead anomaly and b) latest imaging study that does not show any evidence of externalized conductors or other visual lead anomaly

Data will be collected at 6, 12, 18, 24, 30, and 36 months post enrollment and during any unscheduled follow-up visits due to patient symptoms suggestive of or with evidence of lead electrical problems. Additionally, cinefluoroscopy (AP, LAO 45° or the best possible LAO view, RAO 45° or the best possible RAO view) will be performed in all patients to determine the incidence and mechanical progression of externalized conductors at the 12, 24, and 36 month visits.

During any follow-up visits, device data and stored electrograms will be collected. All clinical events such as hospitalizations, emergency room visits, and adverse events will also be collected. All study data, including device data and stored electrograms will be sent to SJM electronically. If any lead being followed in this study develops a significant electrical abnormality suggestive of lead malfunction and x-ray or cinefluoroscopy would be performed as per the site standard of care then copies of x-ray or cinefluoroscopy should be submitted to SJM.

During the course of the study, any explanted leads should be returned to Returned Goods, St Jude Medical, Sylmar, CA, for analysis.

Study Flow Diagram

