3.2.2.7 Time from externalized conductors to clinical intervention

Lead Population

All the leads with externalized conductors within the Riata, Riata ST silicone, QuickSite/QuickFlex (1056T, 1058T, 1156T, 1158), and Durata lead groups

Analysis:

Time to clinical intervention will be analyzed using the Kaplan-Meier method. The zero time will be the date at which externalized conductor was detected. Those patients who experience externalized conductor after enrollment but do not experience clinical intervention will be censored 3 years after enrollment in this trial. A separate Kaplan-Meier curve will be calculated for each of the lead subgroups outlined in Table 2.

For QuickSite/QuickFlex leads only, data from patients with an additional 1 year of follow-up will contribute to 2 separate lead subgroups (See Section 3.4.5).

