- It is recommended that the Stored EGM Configuration be programmed to the following in patients with

Current/Promote or newer devices ICDs and CRT-Ds:

- RV Bipolar
- RV Unipolar Tip
- Custom: RV Coil to Can (optional)

*** Note:** If patient is pacer dependent or R-wave is not available then RV signal amplitude is not required.

Upon completion of the enrollment visit, complete the enrollment case report form (CRF) using the EDC system and submit the supportive data listed below to St. Jude Medical. Contact and address information are available on the last page of the CRF worksheet.

Enrollment CRF

Electronic device session records

Cinefluoroscopy (AP, LAO 45° or best possible LAO view, RAO 45° or best possible RAO view)

Earliest Chest X-ray or imaging study with evidence of externalized conductors or other visual lead anomalies, if available

Latest Chest X-ray or imaging study with no evidence of externalized conductors or other visual lead anomalies, if available

All eligible patients will be required to undergo the protocol specified follow-up visits. Patient participation in the study will be terminated once the 36 month visit is completed or after all leads being followed by the study are extracted and/or abandoned and the patient is monitored for 30 days.

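### For leads found abnormal before enrollment, the detection-to-event curves (3.2.2.4, 3.2.2.5, 3.2.2.7, 3.2.2.8) count event-free time guaranteed by selection as time at risk, so progression looks slower than it is

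*Combined protocol and SAP*

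**What the plan says.** **Time origin.** Section 3.2.2.4 (externalized conductors to electrical dysfunction) states: "The zero time will be the date at which externalized conductor was detected". Section 3.2.2.7 uses the same origin for clinical intervention, and 3.2.2.5 and 3.2.2.8 use the parallel origin for other visual anomalies. By contrast, 3.2.2.1 to 3.2.2.3 and the primary hazard rates (3.2.1.4 to 3.2.1.6) run from enrollment.

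**Population.** For 3.2.2.4: "All the leads with externalized conductors but without electrical dysfunction within the Riata, Riata ST silicone" and the other lead groups. For 3.2.2.7: "All the leads with externalized conductors within the Riata, Riata ST silicone, QuickSite/QuickFlex" and Durata, with no condition on earlier intervention. Neither is limited to findings made after enrollment.

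**Where an early detection date can come from.** Section 3.1 states that "cinefluoroscopy performed as part of separate screening can be used to determine the prevalence of lead compromise as long as all three views" are present, and sets no maximum age. It also asks sites, where available, for the "earliest imaging study showing evidence of externalized conductors or other visual lead anomaly".

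**Entry.** Inclusion criterion 2 (3.3.1) requires an eligible lead that is already implanted. Section 2.0 ties electrical dysfunction to a lead that was capped, extracted or electrically abandoned. Under 11.3 the electrical committee reviews leads taken out of service during the study.

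**Censoring.** The rule in 3.2.2.4 reads: "Those patients who experience an externalized conductor after enrollment, but do not experience an electrical dysfunction will be censored 3 years after enrollment". It covers only findings made after enrollment, as do its counterparts in the other three sections.

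Delayed entry is not mentioned, and the plan does not say which image date counts as detection for a lead already abnormal at enrollment.

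**The concern.** A lead seen to be externalized at a screening cine and extracted before its patient could be enrolled never appears in the data. A lead with the same screening date that stayed in service does appear, and its clock starts at that date. Between detection and enrollment it could not have had the event and still be in the analysis. Ordinary Kaplan-Meier nevertheless places it in every risk set over that interval. The denominators are too large while the numerators are unchanged, so cumulative incidence is too low.

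Section 1.0 says the study will inform physicians whether externalization with normal electrical function may progress to malfunction. Section 3.2.2.4 is the analysis that measures this directly, and the error runs in the reassuring direction. For intervention, Section 3.1 itself expects some physicians to explant recalled Riata and Riata ST leads that function normally; any extracted before enrollment cannot enter.

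**Working it through.** The documents give no expected rate or precision for these four analyses, so there is no stated figure to reproduce.

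**Direction.** At each event time the Kaplan-Meier factor is 1 - d/n. Delayed entry counts in n only leads already enrolled by that time since detection; the ordinary method counts all leads. The d are the same and the ordinary n is never smaller, so ordinary cumulative incidence is never above the delayed-entry value.

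**Size: inputs, all assumed.** Constant hazard h per year from detection; a share f of leads detected before enrollment, with a gap uniform on 0 to G years; a lead enters only if event-free at enrollment; no loss to follow-up.

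**Formula.** The share of detected leads that can enter is D = (1 - f) + f × A, where A = (1 - e^(-hG)) / (hG). For t ≥ G, every lead event-free at t has entered, so the ordinary estimate is 1 - e^(-ht)/D. The truth is 1 - e^(-ht).

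**Main example, h = 0.05, f = 0.5, G = 1.**
- A = (1 - 0.951229)/0.05 = 0.9754; D = 0.5 + 0.5 × 0.9754 = 0.9877.
- 1 year: 1 - 0.9512/0.9877 = 3.69%; truth 4.88%. Shortfall 1.18 points, or 24% of the truth.
- 3 years: 1 - 0.8607/0.9877 = 12.86%; truth 13.93%. Shortfall 1.07 points, or about 8%.

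**Other assumptions, same formula.**

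| h | f | G (years) | t (years) | Ordinary KM | Truth |
|---|---|---|---|---|---|
| 0.05 | 0.25 | 0.25 | 1 | 4.7% | 4.9% |
| 0.05 | 1 | 1 | 1 | 2.5% | 4.9% |
| 0.05 | 1 | 1 | 3 | 11.8% | 13.9% |
| 0.10 | 0.5 | 1 | 1 | 7.3% | 9.5% |

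**Longer gaps, with attrition.** A simulation (400,000 leads per scenario) used exponential gaps with mean L of 0.5 to 2 years, h of 1% to 10% per year, 3 years of follow-up, and the 43% three-year attrition that Section 3.1 expects for Riata/Riata ST. The ratio of ordinary to true 3-year incidence was:
- f = 25%: 0.85 to 0.96
- f = 50%: 0.72 to 0.92
- f = 100%: 0.45 to 0.85
- L = 0: 1.00 within simulation error, so no bias

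On the rate scale, the ordinary rate is h × F/(F + f × L), where F is mean follow-up. With 43% attrition, F = 0.43 × 3/(-ln 0.57) = 2.29 years. For f = 0.5 and L = 1 the factor is 2.29/2.79 = 0.82.

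**Does delayed entry repair it?** In the same simulation the delayed-entry estimate matched the truth within simulation error in every scenario. For h = 3% per year (true 3-year incidence 8.6%) and f = 50%, with L of 0.5, 1 and 2 years, ordinary Kaplan-Meier gave 7.8%, 7.2% and 6.2%; delayed entry gave 8.5%, 8.6% and 8.6%.

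**The case against.** The strongest reply is that the plan never makes a pre-enrollment image the time origin. Under 11.2 the imaging committee adjudicates the enrollment and annual cines, and only adjudicated imaging is reported. Archival films come only if they exist, and an old film re-read after a positive enrollment cine is not naturally something detected on the film's own date. Patients rolled over from the Riata Lead Evaluation Study appear to keep their original enrollment date, judging by the widened 6-month window in Table 4. If every lead abnormal at enrollment is dated from a cine taken at that visit, the bias is zero.

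This stands as a limit but does not remove the point. A separate-screening cine of any age may serve as the baseline itself, and 11.2 also covers additional images received. The plan leaves the choice of date open.

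Three further objections stand:
- **Intervention.** The guarantee is firm only for extraction. A capped lead is still implanted, 3.2.2.7 and 3.2.2.8 do not require leads to be free of earlier intervention, and clinical intervention is not defined.
- **Size.** It rests on assumed inputs, and the relative shortfall falls from 24% at 1 year to about 8% at 3 years in the main example.
- **Remedy.** Requiring the earliest archival image as the origin would let the clock depend on which films happen to survive.

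A reader might also infer that, because "Patient participation in the study will be terminated once the 36 month visit is completed", the curves beyond 24 months rest only on leads abnormal at enrollment. The documents do not support that. Consenting QuickSite/QuickFlex patients continue to 48 months (3.4.5), imaging prompted by an electrical abnormality can detect a finding before month 12, and visit windows are ±60 days.

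**Conclusion.** The point holds conditionally. As written, the four analyses can count selected event-free time as time at risk, and wherever they do, progression after detection is understated. In the main example the shortfall is about 1.2 percentage points at 1 year and 1.1 at 3 years. It could be negligible or considerably larger, because the share of leads detected before enrollment and the length of the gap are not in the documents.

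Two stronger conclusions are tempting. One is that the study's progression curves will be biased; that requires pre-enrollment detection dates actually to be used, which the plan neither requires nor rules out. The other is that the bias is worst for clinical intervention; with that event undefined and some intervened-on leads able to enroll, the documents do not show it.

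The direction is relative to time since detection. Detection lags true externalization, so the net error relative to true onset cannot be determined. These are secondary outcomes; the primary hazard rates start at enrollment and this mechanism does not touch them.

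**What to change.** In 3.2.2.4, 3.2.2.5, 3.2.2.7 and 3.2.2.8:

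1. State which date counts as detection for a lead already abnormal at enrollment, without making the earliest archival image mandatory.
2. If that date can precede enrollment, keep detection as the origin but admit each lead to the risk set only from its enrollment date (left-truncated Kaplan-Meier). Alternatively, start the clock of these leads at enrollment.
3. Extend the censoring rule to them: censor at end of follow-up if no event has occurred.
4. Report leads abnormal at enrollment and leads newly abnormal afterwards as separate curves with numbers at risk. Do not impose a fixed 24-month cut-off, which would discard valid follow-up.

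The cost is SAP wording and one start-time variable; no new data are needed. With delayed entry the early risk sets are smaller and the intervals somewhat wider.

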The Durata® family of ICD leads utilizes a silicone polyurethane co-polymer insulation known as Optim which has been associated with a significant reduction in abrasion when compared to Riata and Riata ST silicone insulated leads. Although the incidence of these insulation abrasion issues is extremely low in Durata leads, the Durata leads are being included in this study for comprehensive

analysis across all St. Jude Medical ICD lead types. This study aims to prospectively determine the prevalence and incidence of lead compromise evidenced by imaging (includes externalized conductors and other visual lead anomalies, by each subcategory, as listed in Appendix A) and electrical dysfunction in patients with Riata, Riata ST silicone ICD, QuickSite/QuickFlex CRT and Durata ICD leads. Prevalence as well as incidence of externalized conductors and other visual lead anomalies will be separately analyzed and reported. In addition, this study will provide information to the physicians regarding the possibility that an observation of externalized conductors with normal electrical function may progress to an electrical malfunction. The SJM Cardiac Lead Assessment Study is sponsored by St. Jude Medical (SJM) and constitutes the modification of the “Riata Lead Evaluation Study”.

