2.0 Purpose

The objectives of the study are:

1. To determine the prevalence of externalized conductors at enrollment in Riata®, Riata® ST Silicone, QuickSite®/QuickFlex® and Durata® leads
2. To determine the prevalence of other visual lead anomalies by each subcategory per Appendix A at enrollment in Riata®, Riata® ST Silicone, QuickSite®/QuickFlex® and Durata® leads
3. To determine the prevalence of electrical dysfunction[§] at enrollment in Riata®, Riata® ST Silicone, QuickSite®/QuickFlex® and Durata® leads
4. To determine the incidence of externalized conductors after enrollment in Riata®, Riata® ST Silicone, QuickSite®/QuickFlex® and Durata® leads
5. To determine the incidence of other visual lead anomalies by each subcategory per Appendix A after enrollment in Riata®, Riata® ST Silicone, QuickSite®/QuickFlex® and Durata® leads
6. To determine the incidence of electrical dysfunction[§] after enrollment in Riata®, Riata® ST Silicone, QuickSite®/QuickFlex® and Durata® leads.
7. To evaluate the 30-day adverse event rate associated with lead revision procedures (include lead extractions or abandonments with or without lead replacement) in Riata®, Riata® ST Silicone, QuickSite®/QuickFlex®, and Durata® families of leads
8. To determine the prevalence of “other insulation anomalies” in “returned leads” for Riata®, Riata® ST Silicone, QuickSite®/QuickFlex®, and Durata® families of leads. “Other insulation anomalies” include any of the following:
 - Internal abrasion short under RV shock coil
 - Internal abrasion short under SVC shock coil
 - Exposed conductors defined as a breach of the outer insulation
 - Breach of the internal silicone lumen tubing, but the conductor cable is contained within the lead body diameter.

[§]”Electrical dysfunction” is determined to be present after adjudication of the following cases of potential electrical failures that led to the lead being either

surgically capped/extracted or electrically abandoned. Potential electrical failures include the following:

- Presence of non-physiologic noise not due to external interference
- Rise in pace/sense (p/s) conductor impedance to $> 2000 \Omega$ or increase of more than 200Ω over previous 6 months or increase of 400Ω over any period of time
- Decrease of more than 200Ω over previous 6 months or to impedance $< 200 \Omega$ from baseline impedance $> 300 \Omega$ or decrease of 400Ω over any period of time

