3.2.3 Additional Data

- Adverse events
- Lead Electrical Measurements: capture threshold, signal amplitude and impedance
- Types of clinical interventions following externalized conductors
- Types of clinical interventions following other visual lead anomalies
- Types of events leading to detection of externalized conductors
- Types of events leading to detection of other visual lead anomalies by each subcategory
- Types of events leading to detection of electrical dysfunction

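### The curves from visual finding to electrical dysfunction can start on images taken because the lead was already abnormal, and the plan never dates dysfunction

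*Combined protocol and SAP*

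**What the plan says.** Section 3.2.2.4 specifies Kaplan-Meier curves by Table 2 subgroup. The population is "All the leads with externalized conductors but without electrical dysfunction within the Riata" and the other three lead groups, and "The zero time will be the date at which externalized conductor was detected". Section 3.2.2.5 has the parallel rule: "The zero time will be the date at which other visual lead anomaly (by each subcategory) was detected". Neither section limits which images can set zero time.

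Section 2.0 says that electrical dysfunction "is determined to be present after adjudication of the following cases of potential electrical failures that led to the lead being either" capped or extracted, or electrically abandoned. Under section 11.3 the electrical committee reviews session records of leads taken out of service.

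Scheduled cines are at enrollment and at 12, 24 and 36 months, with one at 48 months for the QuickSite/QuickFlex extension. Other images also count. Section 3.1 asks for copies if "any lead being followed in this study develops a significant electrical abnormality suggestive of lead malfunction and x-ray or cinefluoroscopy would be performed" under the site's standard of care, and 3.4.2 repeats this. Section 3.4.3 recommends fluoroscopy data at system revision. Section 11.2 has the imaging committee read additional images received during the study as well as the scheduled ones.

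The Introduction gives the purpose: to inform physicians about "the possibility that an observation of externalized conductors with normal electrical function may progress to an electrical malfunction". Section 3.2.3 lists "Types of events leading to detection of externalized conductors" as additional data, but no time-to-event analysis uses it.

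**The concern.** The question is prognostic: given a visible finding in a lead that works normally, how often and how soon does the lead fail? For that, every lead must be electrically normal when its clock starts. The plan's only entry condition is the absence of dysfunction, and dysfunction by definition comes late, after the lead has been taken out of use. A lead with noise or an impedance shift that is still in service can meet that condition. If the abnormality prompted the image, the clock starts because the lead is failing, and its removal shortly afterwards looks like rapid progression. The start of the curve would then mix the risk that physicians want to know with faults that were already under way.

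**Working it through.** **1. Can an abnormal lead enter?**
- An image taken because of an abnormality can be the first to show the finding (3.1, 3.4.2), is adjudicated (11.2), and so can set zero time (3.2.2.4, 3.2.2.5).
- On that date the lead may be abnormal but in service. By section 2.0 it does not yet have dysfunction if dysfunction is dated at removal or adjudication.
- The population wording carries no date. Applied to the whole study it would exclude every event, so it can only mean absence at zero time.

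**2. Does the dysfunction date settle it?** Take a lead with noise at month 14, externalization on the image this prompts, and removal at month 15.
- Dated at removal: the lead enters at month 14 and has an event 15 − 14 = 1 month later.
- Dated at first noise: dysfunction is present at zero time and the lead is excluded.

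The plan does not say which date applies, so the result depends on an undefined rule.

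**3. How large could it be?** The plan gives no event count or rate for these analyses, so there is no figure to reproduce. The following is an illustration only: a Kaplan-Meier simulation of 600,000 leads per scenario.

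From the documents: cines at 0, 12, 24 and 36 months; an event requires the lead to be out of service; censoring at 3 years; prevalence end points of 0.5% and 33.3% (Introduction, for Riata/Riata ST).

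Assumed: a middle prevalence of 20%; new externalization 1% or 5% per year; electrical abnormality 2% or 5% per year; hazard ratio after externalization 1 or 3 (3 only with the 2% rate); triggered imaging in 50% or 100% of abnormal leads; mean delay from abnormality to removal 1 or 3 months; all leads electrically normal at enrollment; event dated at removal.

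Three scenarios at 33.3% prevalence, 5% new externalization per year and 2% abnormality per year. Each cell gives cumulative dysfunction as written / with leads already abnormal at zero time excluded:

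| Scenario | After enrollment, 3 months | After enrollment, 1 year | Pooled, 3 months | Pooled, 1 year |
|---|---|---|---|---|
| HR 1, 50% imaged, 3-month delay | 0.83% / 0.22% | 2.30% / 1.38% | 0.29% / 0.19% | 1.64% / 1.50% |
| HR 1, 100% imaged, 1-month delay | 1.70% / 0.32% | 3.11% / 1.70% | 0.54% / 0.32% | 1.99% / 1.76% |
| HR 3, 100% imaged, 1-month delay | 4.72% / 1.01% | 9.11% / 5.40% | 1.63% / 1.05% | 6.00% / 5.42% |

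In the second row externalization has no effect on failure. Even so, the after-enrollment estimate is 1.70/0.32 = 5.3 times too high at 3 months and 3.11/1.70 = 1.8 times at 1 year. Pooled at 1 year, the ratio is 1.99/1.76 = 1.13.

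Ranges over the scenarios:
- After enrollment: 3 months about 0.8% to 4.9% against 0.2% to 1.1%; 1 year 2.3% to 9.2% against 1.3% to 5.4%.
- Pooled at 20% to 33% prevalence: 3 months 0.3% to 2.1% against 0.2% to 1.1%; 1 year 1.6% to 6.4% against 1.4% to 5.4%.

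**4. Small subgroups.** A Riata subgroup at its Table 2 minimum of 100 leads has 100 × 33.3% ≈ 33 externalized leads at the top of the reported prevalence. If no other lead fails early, 2 leads already failing at detection give 2/33 = 6.1%. In an assumed set of 20 they give 2/20 = 10%.

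**The case against.** The strongest reply is that the bias depends on how dysfunction is dated. The electrical committee reviews session records, which may show onset. If onset is the event date, leads already abnormal at zero time fall outside the population. This stands: a reader might infer that the plan itself records one-month progression in the case above, but the documents leave the date open.

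Four further points also stand, in whole or in part.
- Triggered imaging is not mandated, and every patient has annual cines. A triggered image is the first detection only when the previous cine did not show the finding.
- System revision is a weak route in. If the lead is removed at that revision, detection and removal coincide and the population wording can be read as excluding it.
- A reader might infer that a few triggered detections multiply the overall risk several times. No counts in the documents support that, and the pooled one-year illustration does not show it.
- A reader might infer that the plan makes externalization look more predictive of failure than it is. Sections 3.2.2.4 and 3.2.2.5 have no comparator and no test. Association with dysfunction is examined in 3.2.2.10, a separate analysis that this point does not address.

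The reply does not close the gap. Possible use of onset dates is not a rule, and nothing in 3.2.2.4 or 3.2.2.5 requires the normal electrical function that the Introduction specifies.

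**Conclusion.** The point holds in a conditional form. Zero time is any detection, the only exclusion is an outcome defined by removal from use, and the outcome has no date. If dysfunction is dated at removal or adjudication, leads imaged because they were already abnormal count as early progression, and the curve does not answer the stated question.

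The documents do not give the size. On the assumed rates, the inflation sits mainly in the first months and in leads first seen with the finding after enrollment. It is modest where most findings come from the enrollment cine, roughly 1.1 to 1.2 times at one year in the pooled curve (1.6/1.4 and 6.4/5.4, comparing range ends). That modest figure rests on leads being electrically normal at enrollment, which the plan does not require. Where few findings are present at enrollment, the pooled curve approaches the after-enrollment one. In small Table 2 subgroups, one or two such leads may matter.

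**What to change.** In 3.2.2.4 and 3.2.2.5:

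1. Define the date of dysfunction, for example the first session record or measurement showing the failure that was later adjudicated. Exclude leads whose date is on or before zero time.
2. Base the main curve on findings first seen at the enrollment cine or a scheduled annual cine, in leads with no section 2.0 potential-failure criterion recorded on or before that date. State the limits of this check: high-voltage impedance testing is optional on older devices and not applicable to CRT-P, and abnormalities in leads still in service are not adjudicated. Some exclusions may therefore reflect external noise or header-connector causes.
3. Report leads first detected on abnormality-triggered images or at system revision as a separate concurrent-detection group, using the detection reason listed in 3.2.3.
4. Keep the all-detections curve as written as a sensitivity analysis, with its event date stated.

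This needs no new visit or image, because detection reasons, lead measurements and session records are already collected. The electrical committee would need to record an onset date if its form does not already do so; the documents do not show the form. The price is fewer leads and events in the main curve. Leads that externalize and fail quickly between annual cines would appear only in the separate group and the sensitivity analysis, so the main curve should be read with both.
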